## **Inclusion Criteria:**

- Be aged 18 and older
- Be capable of giving informed consent themselves and are able and willing to participate in the study
- Patients willing to forgo any optional dental procedures during the study period, such as dental prophylaxis or teeth whitening
- Patients that regularly brush their teeth twice a day

# **Exclusion Criteria:**

- Pregnant or breastfeeding women
- Patients taking long-term anti-microbial or anti-inflammatory drugs
- Patients unable or unwilling to provide informed consent
- Self-reported use of tobacco products
- Gross oral pathology, including widespread caries or chronic neglect, extensive restoration, pre-existing gross plaque or calculus, or soft or hard tissue tumor of the oral cavity
- Less than 26 teeth in the mouth
- Orthodontic appliances or removable partial dentures that will compromise the ability of the potential subject to participate in the study
- Periodontitis as indicated periodontal pockets greater than 5 millimeters on more than one site
- Inability to comply with assigned treatment regimen

# Randomization and allocation:

Randomization will be carried out using a computer-generated random allocation

table assigning the participants to one of study groups as follows:

Arms	Assigned Interventions
Experimental: CPC 0.09% +	Dietary Supplement: CPC 0.09% + Xylitol
Xylitol chewing gum A	

		All subjects will be instructed to chew four times a
		day, for at least 60 seconds, after which they
		expectorated.
		Other Name: CPC-Xylitol complex
Experimental: Xy	litol only	Dietary Supplement: Xylitol
chewing gum B		All subjects will be instructed to chew four times a
		day, for at least 60 seconds, after which they
		expectorated.
		Other Name: Xylitol only

Half of the eligible participants will be randomly assigned to get CPC gum in the first treatment period (21 days), a wash-out period of 21 days, and then a placebo gum in the second treatment period (21 days). The other half would be assigned to follow the same schedule but with the treatment reversed. A statistician will perform the randomization whereas the project leader will distribute the chewing gums and instructions after a list generated as described.

# C. Outcomes:

# Primary outcome:

The primary outcome of interest in this study is the efficacy of the antiplaque chewing gum in reducing existing supragingival plaque and gingivitis will be assessed.

**Plaque Index** - Plaque will be assessed using the Turesky Modification of the Quigley-Hein Plaque Index(Turesky, Gilmore, and Glickman 1970), where a score of 0 to

5 will be assigned to each facial and lingual non-restored surface of all teeth that are present with the exception of third molars at baseline and week 3 of the study, as follows:

Scores	Criteria
0	No plaque
1	Separate flecks of plaque at the cervical margin of the tooth
2	A thin continuous band of plaque (up to one mm) at the cervical margin of the tooth
3	A band of plaque wider than one mm but covering less than one- third of the crown of the tooth
4	Plaque covering at least one-third but less than two-thirds of the crown of the tooth
5	Plaque covering two-thirds or more of the crown of the tooth

Gingivitis will be assessed using both the Gingival Index (GI), where a score of 0 to

3 will be assigned to six teeth, representing six segments of jaws, at baseline and week 3

of the study according to the following criteria:

Scores	Criteria
0	Absence of inflammation.
1	Mild inflammation - slight change in color and little change in texture.
2	Moderate inflammation - moderate glazing, redness, edema, and hypertrophy. Bleeding on pressure.
3	Severe inflammation - marked redness and hypertrophy. Tendency to spontaneous bleeding. Ulceration.

In addition, the percent of bleeding sites on probing (BOP)(Ainamo and Bay 1975) as described in Ainamo & Bay, 1975, where each of 4 gingival areas (disto-buccal, midbuccal, mid-lingual, and mesio-lingual) around each tooth will be light probed and scored from 0 to 2 as follows:

Scores	Criteria
0	Absence of bleeding after 30 seconds
1	Bleeding after 30 seconds
2	Immediate bleeding

## Secondary Outcomes:

Changes from baseline to post-baseline efficacy assessment will be recorded for all parameters.

The antiplaque **chewing gum safety** will be evaluated; the oral soft (OST) and oral hard tissues (OHT) will be examined. Changes from baseline, such as soft tissue erythema, ulceration, and sloughing, will be noted and assessments will be made by the principal investigator as to whether they might be attributable to the antiplaque chewinggum.

Objective observation of **Discoloration of teeth** will be recorded using a Vita 3D scale. Changes on baseline (day 1) and day 22 and will be annotated as none, slight to obvious.

## Study period:

The study period will be comprised of two periods of 21 days with a washout period in between. In each 21 days' period, there are three study visits: 1) Baseline Day

1, 2) Day 11 (after ten days of use), and 3) Day 22 (after 21 days of use – completion of the study). An additional screening visit will be required, and may or may not be combined with baseline visit, according to patients' preference.

#### Statistical analysis:

The Primary Aim is to evaluate the change in in the score of PI, GI, and BOP averaged across the teeth between the CPC based chewing gum and the placebo gum at day 21. Assume there is no carryover effect and no interactions between patients, treatments, and periods; a paired t-test is used to compute the sample size. To detect an effect size for CPC based chewing gum on the changes in the three outcomes at day 21 relative to baseline, with a within-subject correlation of 0.3 and a significance level of 0.05, the study requires 62 participants to achieve 80% power after Bonferroni correction for three tests. Considering a dropout rate of 15%, we need to recruit 73 participants.

Linear mixed model will be used to evaluate treatment effects on the three primary outcomes at day 21 compared to baseline independently, with Bonferroni correction. If normality of the outcomes does not hold, appropriate transformation or generalized estimating equation method can be used. Furthermore, the three outcomes could be analyzed simultaneously while accounting for the within-subject correlation. Similar analyses will be done for the secondary outcomes including changes from baseline to post-baseline efficacy assessment for day 21. Longitudinal data analysis will be used to analyze the data through day 0, 10, and 21, to see the pattern of the outcomes. Descriptive statistics will be provided for safety data. All analyses will be performed in SAS 9.4 (Cary, NC).

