#### **Study Population**

Test group will be composed of up to 73 dental, dental hygiene students, faculty, and staff, who will be recruited from the University of Texas Health Science Center at Houston School of Dentistry (*UTHealth School of Dentistry*). Those, who meet the inclusion criteria for the study, will meet with the investigators for additional information about the study and informed consent.

Plaque Index (PI)(Löe and Silness 1963) and Gingival Bleeding Index (GBI)(Lobene et al. 1989) and bleeding sites on probing (BOP) (Newbrun 1996) will be recorded at baseline for all selected subjects. After assessment, subjects will undergo oral prophylaxis to bring the plaque levels to zero. After oral prophylaxis subjects will be instructed on the proper brushing technique (Modified Bass techniques) and will be given either the test chewing gum or placebo formulation. The chewing gums will be packaged in similar fashion labeled only as sample A and sample B to ensure proper blinding of the product from the subjects and the examiner. All chewing gums will be supplied by Confadent oral technology, which will be sponsoring the current study. The test and control chewing gum will be dispensed to subjects along with a diary to record product usage and daily oral hygiene activity. All the subjects in both the groups will be given a soft bristled toothbrush and dental floss for use during the study. The study groups will be asked to refrain from all other unassigned forms of oral hygiene for the duration of the study. After four weeks, subjects will be recalled. GBI and PI will be evaluated at the end of 4 weeks using same indices.

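### The plan frames its primary comparison as change from baseline and names no baseline covariate; adjusting the day-21 score for each period's Day 1 score would be more efficient at no cost in participants

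*Combined protocol and SAP*

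**What the plan says.** All of this is in the Statistical analysis section of the combined protocol and SAP, except where noted.

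- **Sizing method:** "a paired t-test is used to compute the sample size", under an assumption of no carryover and no interactions.
- **Quantity sized on:** an effect "on the changes in the three outcomes at day 21 relative to baseline". The aim is likewise worded as a change in plaque index, gingival index and bleeding on probing. An effect size is mentioned ("To detect an effect size for CPC based chewing gum on the changes in the three outcomes"), but no value and no SD are given.
- **Assumptions and result:** "with a within-subject correlation of 0.3 and a significance level of 0.05, the study requires 62 participants to achieve 80% power". The Bonferroni adjustment covers three tests. Recruitment is 73, allowing for 15% dropout. The plan does not say which two measurements correlate at 0.3, and gives no source for it.
- **Primary analysis:** a linear mixed model for each outcome, setting day 21 against baseline. It does not say whether baseline is subtracted, entered as a covariate or treated as a repeated measure.
- **Baselines:** the Study period section gives each 21-day period its own Day 1 visit, so every participant has two baselines and two day-21 scores.
- **Prophylaxis:** the Study Population section says "After assessment, subjects will undergo oral prophylaxis to bring the plaque levels to zero".

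**The concern.** The gum contrast, as sized, is a difference between two change scores. Subtracting Day 1 assumes that a one-point difference between a person's two baselines carries through as a one-point difference at day 21. If the true slope is below 1, subtraction adds noise from the baselines to the contrast. This matters most for plaque: the Day 1 score is taken before a cleaning intended to remove all plaque, so it may predict the day-21 score only weakly.

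What is at stake is precision. The Day 1 scores are collected anyway, and a model that estimates their slope uses them better than one that fixes it. Because the section leaves the handling of baseline open, a change-score analysis is a natural way to carry it out.

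**Working it through.** **Inputs.** From the Statistical analysis section: 62 evaluable participants, 80% power, correlation 0.3, overall alpha 0.05, three tests, 15% dropout. Assumed: two-sided testing, so alpha is 0.05/3 = 0.01667 per outcome, and an effect of 0.5 SD. Power is from the noncentral t distribution with 61 degrees of freedom and noncentrality dz × √62, where dz is the effect divided by the SD of the within-person contrast.

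**Step 1: reproduce the plan's figure.** If the two changes correlate at 0.3, the contrast has variance 2(1 − 0.3) = 1.4 in units of the change variance. Solving for 80% power at n = 62 gives dz = 0.421, so d = 0.421 × √1.4 = 0.498. With d = 0.5, dz = 0.5/√1.4 = 0.423, power is 80.4% and the required n is 62. Dropout: 62/0.85 = 72.9, so 73. The plan's figures reproduce on this reading.

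**Step 2: compare subtraction with adjustment.** Let scores have unit variance. Write w for the correlation of Day 1 with day 21 in the same period, b for the same visit across periods, and c for different visits across periods. Put D = 1 − b and e = w − c.

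- Change-score contrast: variance 4(D − e).
- Day-21 contrast adjusted for the difference between the two baselines: variance 2D − 2e²/D = 2(D − e)(D + e)/D.
- Ratio, adjusted to change: (1 + r)/2, where r = e/D is the correlation between the baseline difference and the day-21 difference.

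The ratio cannot exceed 1. It is one half when r = 0 and approaches 1 only as r approaches 1. The estimated slope costs one degree of freedom, under 0.1 percentage point of power here.

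**Step 3: changes correlate at 0.3, effect 0.5 SD of the change.** The correlation of the changes is (b − c)/(1 − w). Setting it to 0.3 gives c = b − 0.3(1 − w). Over w from 0 to 0.7 and b from 0.2 to 0.7, keeping admissible combinations, the least favourable is w = 0.7, b = 0.2, c = 0.11:

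- r = 0.59/0.80 = 0.7375 and the ratio is 0.869.
- The adjusted variance is 1.4 × 0.869 = 1.216, so dz = 0.5/√1.216 = 0.453.
- Power is 86%, against 80.4% for change scores.

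Every other admissible case checked gives more.

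**Step 4: all cross-period correlations 0.3 (b = c = 0.3), effect 0.5 SD of the score.**

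| w | Variance, change | Variance, adjusted | Power, change | Power, adjusted |
|---|---|---|---|---|
| 0.3 | 2.8 | 1.400 | 46% | 80% |
| 0.5 | 2.0 | 1.286 | 63% | 84% |
| 0.7 | 1.2 | 0.943 | 87% | 94% |

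**Step 5: same correlations, effect 0.5 SD of the change.** Change-score power is 62.7% throughout. Adjusted power is 92.6%, 84.0%, 74.9% and 70.6% for w = 0.3, 0.5, 0.7 and 0.8. Adjustment is better in each case, but it does not guarantee 80%.

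**The case against.** The strongest objection is that nothing in the plan is shown to be wrong. The sizing sentence attaches 0.3 to the changes, a paired t-test needs the correlation between the paired quantities, and on that reading 62 participants give 80.4%. This stands.

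A reader might infer more than the documents support, in three ways.

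- **That true power is 46–63%.** This takes 0.3 as the correlation between a person's scores. The changes are then uncorrelated only if same-visit and different-visit correlations across periods are equal, which the plan does not state. With w = b = 0.3 and c = 0.09 the changes correlate at (0.3 − 0.09)/0.7 = 0.3. The range also mixes two SD scales. Nor does zero correlation between changes fix power in that range: in the last row of the Step 4 table the changes are uncorrelated and change-score power is 87%.
- **That prophylaxis drives the correlation of the changes to zero.** It need not. If cleaning broke the link between Day 1 and day 21 (w = c = 0) while b stayed at 0.3, the changes would correlate at exactly 0.3. A weak link is a reason to estimate the slope, not evidence against the sample size. The passage also speaks only of plaque, not gingival index or bleeding, and does not mention a second prophylaxis before period 2.
- **That the plan has chosen the less efficient analysis.** The paired t-test on changes is the sizing device. The mixed model leaves the role of baseline open and could be run with a covariate.

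It is also fair to object that the benefit depends on correlations nobody has reported. Its size does; its direction does not.

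**Conclusion.** The point holds as a free improvement in the analysis, not as a power error. Adjusting for each period's Day 1 score is at least as precise as subtracting it under any correlation structure, apart from one degree of freedom. Where the two changes correlate at 0.3, power rises from 80.4% to at least 86% over the structures checked. Where all cross-period correlations are 0.3 and the effect is in score SDs, it is 80%, 84% and 94% against 46%, 63% and 87%.

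These figures rest on an inferred effect of 0.5 SD, two-sided tests at 0.05/3, 62 completers, equal variances at all visits and the correlations stated. The gain shrinks as the baseline difference becomes a strong predictor of the day-21 difference.

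The plan's 80% is conditionally reproduced and should not be called wrong. The effect size, its scale and the meaning of 0.3 do need to be stated, because the calculation cannot be checked without supplying them.

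**What to change.** In the Statistical analysis section:

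1. For each primary outcome, make the day-21 score the response in the linear mixed model, with treatment, period and that period's Day 1 score as fixed effects and subject as a random effect. The within-person gum contrast is then adjusted for the difference between the two baselines. Adding each person's mean of the two Day 1 scores as a further covariate keeps the slope wholly within-person, which is the analysis the figures above describe.
2. State the effect size used (0.5 SD of the change, if that was intended), its SD scale, and that tests are two-sided, if so.
3. State which two measurements the 0.3 joins, and its source.
4. Do not add a statement that power is 46–63%, or that the adjusted analysis guarantees 80%.

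The cost is a few sentences and about one degree of freedom (two with the mean-baseline term). No extra participants, visits or measurements are needed. The wording should be settled before unblinding.

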## B. Research design and methods:

#### **Study Design**

This study is a placebo-controlled, double-blind, randomized crossover study to evaluate the plaque and gingivitis reducing capacity of Cetylpyridium Chloride (CPC) based chewing gum.

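### Optional improvement: Holm's step-down rule in place of plain Bonferroni keeps the 5% family-wise error and, if all three primary outcomes respond equally at about 0.5 SD, raises per-outcome power from 80% to about 85-89%

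*Combined protocol and SAP*

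**What the plan says.** The trial is a two-period crossover of CPC gum against placebo gum. Three primary measures, Plaque Index (PI), Gingival Index (GI) and bleeding on probing (BOP), are compared at day 21.

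Bonferroni appears twice in the Statistical analysis section. The sizing sentence says "the study requires 62 participants to achieve 80% power after Bonferroni correction for three tests", with "a within-subject correlation of 0.3 and a significance level of 0.05". The analysis sentence says the mixed model will "evaluate treatment effects on the three primary outcomes at day 21 compared to baseline independently, with Bonferroni correction". No step-down or other sequential rule is mentioned.

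The size of effect is not given; the text says only "To detect an effect size for CPC based chewing gum on the changes in the three outcomes at day 21 relative to baseline". Sidedness and the correlation between the three outcomes are not given either.

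Under Primary outcome, the three measures are built differently. Plaque is scored 0 to 5 and "will be assigned to each facial and lingual non-restored surface of all teeth that are present" (third molars excepted). GI is scored 0 to 3 and "will be assigned to six teeth, representing six segments of jaws". Bleeding is scored 0 to 2 at four areas around each tooth.

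**The concern.** Under plain Bonferroni each outcome must reach 0.05/3 = 0.0167 whatever the other two show. Holm orders the p-values and compares the smallest with 0.05/3, the next with 0.05/2 and the largest with 0.05, stopping at the first failure. Its first step is the Bonferroni step, so it can never reject less, and its error guarantee needs no assumption about how the outcomes are correlated. It needs only p-values, so it works equally with the mixed model, a transformed outcome or the GEE fallback.

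The plan sizes the trial on 80% power after correction and tests the outcomes separately, so power per outcome is a natural yardstick. Holm raises it with no extra participants or visits. The three indices differ in scale and in the teeth sampled, so equal effects cannot be taken for granted, and Holm helps a weaker outcome most.

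**Working it through.** **Inputs from the plan:** overall alpha 0.05; three tests; within-subject correlation 0.3; paired t-test for sizing; 62 evaluable; 15% dropout.

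**Assumptions:** two-sided tests; effect size back-solved from 62; between-outcome correlation from 0 to 0.9.

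**1. Reproduce the plan's figure.** In units of the SD of the per-period change, the paired difference has SD √(2(1 − 0.3)) = √1.4 = 1.183. An effect of 0.5 SD is then 0.5/1.183 = 0.423 SDs of the difference. The exact noncentral-t power at two-sided 0.05/3 is 0.804 at n = 62 and 0.796 at n = 61, so 62 is the smallest n reaching 80%. It is the smallest n only for effects of about 0.498 to 0.502; 0.45 would need 76 and 0.55 would need 52. Dropout: 62/0.85 = 72.9, hence 73. The plan's figures are reproduced with an effect of 0.5 SD.

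**2. Bounds on the gain.** At n = 62 and 0.5 SD, power for one outcome is 80.4% at 0.05/3, 84.5% at 0.05/2 and 90.6% at 0.05. Per-outcome power under Holm must lie between 80.4% and 90.6%.

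**3. Holm against Bonferroni by simulation.** 100,000 trials per scenario, n = 62, three equicorrelated paired differences with SD √1.4, correlations 0, 0.3, 0.5, 0.7 and 0.9. Exact Bonferroni power is 80.4% at 0.5 SD, 45.2% at 0.35 and 22.1% at 0.25.

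| True effects (SD) | Holm result over correlations 0 to 0.9 |
|---|---|
| 0.5 / 0.5 / 0.5 | each 88.8, 87.7, 87.2, 86.4, 85.0% |
| 0.5 / 0.5 / 0 | real effects 83.8, 83.5, 83.3, 83.0, 82.6% |
| 0.5 / 0 / 0 | gain 0.03 to 0.14 points |
| 0.5 / 0.35 / 0.35 | strongest 84.8 down to 80.5% (gain 4.4 to 0.1 points); weaker two 55.6 to 56.2% (gain 10.5 to 10.7) |
| 0.5 / 0.25 / 0.25 | strongest gains 2.0 to 0.0 points; weaker two 28.7 to 30.6% (gain 6.5 to 8.6) |
| 0.5 / 0.35 / 0.25 | gains 3.2 to 0.1, 8.0 to 6.7 and 8.9 to 13.7 points |
| 0.35 / 0.35 / 0.35 | each 51.5 to 52.8% (gain 6.1 to 7.5) |

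With three equal effects of 0.5 SD, the chance of at least one significant outcome is the same under both rules: 99.2, 97.4, 95.4, 92.5 and 87.6% across the five correlations.

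**4. Error rate.** With no real effect, Holm's family-wise error was 0.050, 0.047, 0.045, 0.039 and 0.030, the same as Bonferroni's. With one real effect it was 0.046 down to 0.031, and with two 0.042 down to 0.035. No trial in any scenario was rejected by Bonferroni but not by Holm.

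**5. Costs.** With two real effects, the false-positive rate on the third outcome rises from about 1.7% to 3.5-4.2%. An outcome significant under Holm has a Bonferroni interval that includes zero in 23.3, 20.4, 18.1, 15.6 and 11.2% of trials when all three effects are 0.5 SD, and in 14-23% in the unequal scenarios.

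**6. Extreme correlation.** A separate simulation (60,000 trials per scenario) agreed. It gave 84.0% at a between-outcome correlation of 0.95 and 81.3% at 0.999, so the gain almost disappears if the outcomes are near copies of each other. At a correlation of 0.5, power to win on all three outcomes rose from 61.5% to 77.8%.

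**The case against.** The strongest reply is that the plan has no defect here. It names one valid correction and uses it consistently in sizing and analysis, so another valid procedure is a matter of preference. That stands, and it is why this is offered as an option only.

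Second, the benefit depends on a success rule the plan never states. If any one outcome suffices, Holm gains nothing. If all three must be significant, no multiplicity adjustment is needed: at 0.5 SD and correlation 0.5, all-three power is about 79% testing each at 0.05, against 78% under Holm and 62% under Bonferroni. This also stands as a limit. But correcting for three separate tests fits a plan that wants a claim on each outcome, and there Holm is better than Bonferroni.

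Third, the 85-89% figure rests on equal effects and on a back-solved effect size. That is correct, so it is given here with those conditions and the unequal scenarios beside it.

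Fourth, the gums are packaged as sample A and sample B while the arm table says which letter is CPC, so it may be unclear when unblinding occurs. The table does not reveal which order any participant was allocated, so a pre-unblinding deadline still works. It is sensible to define it by access to outcome data split by gum label or treatment.

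Finally, the plan says secondary outcomes will be analysed similarly and allows a joint analysis of the three outcomes. An amendment should say which family Holm covers.

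**Conclusion.** The point holds as an optional, low-cost improvement; the Bonferroni analysis is not wrong. Under two-sided paired tests, n = 62, within-subject correlation 0.3 and between-outcome correlations of 0 to 0.9, Holm raises per-outcome power from 80% to 85-89% if all three effects are 0.5 SD and to 83-84% if two are, and leaves it unchanged if only one is. With unequal effects, the strongest outcome gains at most 4.4 points in the scenarios examined, and the weaker ones about 6.5 to 13.7. Family-wise error stays at or below 5%. The main uncertainty is the unstated effect sizes and between-outcome correlation, which decide how the gain is shared.

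**What to change.** In the mixed-model sentence of the Statistical analysis section, replace the Bonferroni phrase with: *with the Holm step-down procedure at overall two-sided 0.05*. State that the family is the PI, GI and BOP comparisons at day 21. Fix this in a dated amendment before unblinding, and before anyone sees outcome data split by gum label or treatment. If any treatment code has already been broken, keep Bonferroni.

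Leave the sample size paragraph as it is: the Bonferroni-based 62 evaluable and 73 recruited become a conservative floor.

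The cost is one phrase plus the line naming the family; sample size and visits do not change. The amendment should acknowledge two downsides. If Bonferroni-adjusted intervals are reported (the plan mentions none), they may include zero for an outcome that Holm declares significant. And when two effects are real, the false-positive risk on the third is higher than under Bonferroni, though still under 5%.
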